Depression and anxiety: Depression and anxiety will be assessed using the *Brief Symptom Inventory*, a 12-item survey that provides subscales severity indexes for depression and anxiety. The *Brief Symptom Inventory* was internally consistent (reliable); in patients with ischemic heart disease (Doering, et al., 2010). The *Brief Symptom Inventory* has been used to assess depression and anxiety in multiple patient populations, including cardiac diseases, and results were found to predict mortality (Doering, et al., 2010). The survey uses simple statements and a 5-level Likert-type response set, ranging from 0, *not at all* to 4, *extremely*.

Pain: Pain is a subjective symptom best measured by self-report. Pain will be measured in 2 ways. (1) Pain intensity will be measured on a scale of 0-10 with a score of 0 for no pain and 10 for worst pain, as part of usual care. (2) Highest (worst) and lowest (least) pain in the past 24 hours will be assessed via pain scores recorded in EPIC.

Sleep: The Richards-Campbell Sleep Questionnaire (RCSQ) was developed in 2000 to overcome issues with other sleep questionnaires used in an acute or ICU setting. Permission was previously given to the mentor of this study ([name]) to use the tool unconditionally. This tool has 5 domains: sleep depth, falling asleep, number of awakenings, percent of time awake, and overall quality of sleep. It uses a visual analog

scale to measure domains of sleep and the composite score range is 0 to 100 (to reflect 0 to 100 mm). The RCSQ is calculated by dividing the sum of the total length in millimeters of the visual analog scale lines by 5. It is reliable with a Cronbach's alpha of .90 in 70 critically ill subjects (Richards, O'Sullivan & Phillips, 2000). It is short, simple, and easy to administer and analyze. This tool will take approximately 1 minute to complete.

Hospital length of stay: Data will be collected by analysts using EPSi administrative database.

New onset atrial fibrillation: Data will be retrieved from the Cardiothoracic Surgery database, led and managed by HVI Institute. It is IRB approved and data are collected on every open-heart surgery as part of the Society of Thoracic Surgery data collection, that Cleveland Clinic participates in. Data will be received in an excel file and encounter record numbers will be matched to questionnaire data for analysis.

All cause 30-day hospital readmission: Data will be collected by analysts using EPSi administrative database.

Narcotic drug burden (mean dose) on postoperative days 3 and 4: Data will be collected via an electronic medical record pull, using our Pharmacy's database. Of oral narcotics, Percocet (acetaminophen and oxycodone) is most commonly used; however, if another oral agent or IV agents are used (for example, fentanyl or dilaudid [hydromorphone]) we will create a drug dose equivalency table so that data are analyzed based on equivalent doses of different agents used.

Patient and medical characteristics: Data will be retrieved from the Cardiothoracic Surgery database, led and managed by HVI Institute. It is IRB approved and data are collected on every open-heart surgery as part of the Society of Thoracic Surgery data collection (version 2.81, effective, 04-23-2015; www.STS.org), that Cleveland Clinic participates in. Data will be received in an excel file and encounter record numbers will be matched to questionnaire data for analysis. This data will be used to compare groups for symmetry. Data collection will include the factors highlighted on the Appendix form; attached and marital status, from the EPSi (billing) database.

Reiki/manual therapy practitioners: Number of practitioners who applied Reiki/manual therapy during the intervention.

Data Collection Procedures

From the "To Come In" (TCI) list for first time cardiac surgery patients, data collectors will retrieve names and interview patients that meet criteria for research and offer the study to patients while they are in the TCI area for surgeries that are planned for upcoming Monday's and Tuesday's, so that consent is given prior to their surgery date. Alternately, we will enroll potential patients in the pre-cath area of J2 when they are in for a cardiac catheterization as part of their upcoming survey.

Written consent will be acquired by patients before initiation of the research study. Research nurses or research coordinators, who are not involved in the intervention or in clinical patient care will administer the questionnaire packets preoperatively (in TCI) and after the last Reiki treatment or usual care day of the research intervention for the following data: anxiety and depression and sleep. After preoperative data collection, patients will be randomized to the usual care or intervention group: using envelopes with assignments (136 control subjects 136 experimental subjects); based on groups of 20. Packets will be created by a nurse from the Office of Research and Innovation and envelope assignments will not be shared with any researcher. Research nurses or research coordinators can assist patients with completion of baseline and post-intervention questionnaires, as desired.

Data retrieved from administrative, EPIC and cardiothoracic surgery databases will be requested using usual procedures, after patients have completed the study. The cardiothoracic surgery database is IRB approved.

Sample Size

Depression and anxiety are the primary outcomes. In a study of healing touch among hospital patients recovering from cardiac surgery (MacIntyre et al, 2008), those who received healing touch had a 71% greater change in “anxiety” score, compared to control subjects (mean decreases: healing touch, 6.3 [2.0, 10.6] and control group, 1.8 [-2.6, 6.2], $p=0.01$). For this research study, we are hypothesizing that Reiki and manual therapy will result in a *30% greater reduction of depression and anxiety* compared to patients in the usual care group. A rate of 30% was selected based on previous research findings: In a cohort of patients who received surgical procedures, postoperative anxiety BSI had a mean of 0.51 and a standard deviation of 0.56, and depression BSI had a mean of 0.42 and a standard deviation of 0.56 (Mackay, Hansen, & McFarlane, 2004). Given the skewed nature of these data, a lognormal distribution was assumed, with a coefficient of variation (standard deviation/mean) of 1.35, based on the depression BSI results above. We believe that a 30% reduction in mean depression and anxiety scores would be clinically important. Based on use of a two-sided two-sample t-test with significance level of 0.05, with adjustment for use of analysis of covariance based on an assumed small positive correlation between baseline and follow-up ($\rho=0.25$) as described by Borm et al. (2007), a sample size of 123 per group would provide 80% power to detect this difference. To account for loss-to-follow-up, recruitment was increased by 10%, creating a sample size of 136 patients per group (272 patients in total). Sample size calculations were performed using SAS software (version 9.4; Cary, NC) by [name] MS of QHS.

Data Analysis

Patient characteristics will be summarized using frequencies and percentages for categorical measures, and means and standard deviations or medians and quartiles, as dictated by the distribution of these measures.

Anxiety, depression and sleep analyses: an analysis of covariance models will be fit, using the follow-up score as the response and patient group and baseline levels of the outcome measure as predictors by using the Brief Symptom Inventory (BSI).

Pain, LOS and other continuous factors: will be compared between groups using analysis of variance models. In each of the models, normality of the outcomes will be evaluated and, if necessary, data will be transformed prior to analysis. Results will be back-transformed for presentation of mean differences with 95% confidence intervals.

Reduced new onset of atrial fibrillation and reduced 30-day hospital readmission are binary outcomes that will be evaluated using Pearson chi-square tests or Fisher exact tests, in the case of rare outcomes.

Exploratory analyses will evaluate the relationship between patient characteristics and outcomes and adjust treatment group differences for these factors using similar methodology. An analysis will be performed using SAS software (version 9.4; Cary, NC). A significance level of 0.05 will be assumed for all outcomes.

Feasibility

The facility has sufficient trained Reiki certified practitioners to provide these modalities safely and accommodate the sample size. Hand placements and manual therapy specific for this study will be conducive for this patient population and will not put the patient at risk. The facility does at least ten cardiac surgeries Monday through Friday specific for this study to meet criteria for sample size.

Limitations and Anticipated Problems

Patients may be off the floor, busy with another service, sleeping or too sick (worsening status, readmitted to the ICU, intubated and sedated) or nauseated to be approached to carry out the Reiki intervention, even after enrollment. Not all patients will receive 3 sessions. To make up for possible attrition, 10% will be added to the minimum sample size. Patients may refuse therapy (a rare occurrence) or may not complete questionnaire tools. Administrative and cardiovascular registry data will be used to collect most variables. If there is a delay in data collection or entry into the database, we may be delayed with analysis.

Human Subjects Protection

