Objectives: Reiki is an energy-based healing therapy using light touch. Manual therapy is a technique using light effleurage. These complimentary healing services are utilized to promote relaxation, sleep, improve emotions, and decrease pain. After reviewing the Reiki research literature, more research is required since sample sizes were small, subjects were generally healthy (not hospitalized), and subjects had multiple medical backgrounds. Only 1 study focused on cardiac surgery patients. In the current research study, we aim to learn if Reiki and manual therapy enhances postoperative clinical outcomes for patients after first time coronary artery bypass graft (CABG) and/or cardiac valve surgery. **Design and Methods:** A randomized, controlled non-blinded study will be used. The sample size (272 total; 136 per group) was based on a power analysis using the primary outcome. The intervention group will receive usual care plus Reiki and manual therapy, with Reiki being delivered first. Hand placements include: head, chest, shoulders, hands, knees, and feet for 15 minutes. Manual therapy will consist of light effleurage to the head and feet for 5 minutes. Total therapies time is 20 minutes. Reiki and manual therapy will be delivered for 3 consecutive days beginning on the day after endotracheal tube removal. The usual care group will receive rest, which is part of usual postoperative care. There will not be a sham-treatment group, based on previous research findings when a sham group was used. **Outcome Measures:** depression and anxiety (*Brief Symptom Inventory*, 12-item self-administered tool); pain (self-reported and recorded in EPIC by staff nurses as part of usual care -- 0 [no pain] - 10 [worst pain] scale), highest (worst) and lowest (least) pain in the past 24 hours will be assessed; night time sleep (Richards-Campbell Sleep Questionnaire; 5 item self-administered tool)—to be measured at baseline and after the last Reiki/manual therapy treatment or 3 days of usual care. Hospital length of stay and all-cause 30-day hospital readmissions will be pulled from the billing database, [narcotic drug burden \(mean dose\) use on postoperative days 3 and 4 will be obtained from electronic medical records](#), and data on patient characteristics, medical history, surgical procedure, new onset atrial fibrillation and other post-operative complications will be retrieved from the IRB-approved Cardiothoracic Surgery database.

Purpose and Research Questions

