Integrative therapies have gained much support and interest in the literature as methods to help alleviate pain and anxiety (Anderson & Cutshall, 2007). However, very few studies revealed therapeutic benefits of massage therapy in patients post CABG surgery (Anderson & Cutshall 2007), including research conducted previously on this patient population at Cleveland Clinic (Albert et al., 2009) that include massage to arms, legs and back. Cardiac surgery patients undergo a long procedure, may experience back, shoulder, and neck pain, or generalized tension postoperatively (Anderson & Cutshall, 2007). In a pilot study (n=58), 1 session of 20 minutes of massage therapy offered between day 2 and 5 postoperatively reduced pain, anxiety and tension scores and patients provided positive feedback (Cutshall, et al, 2010). Although authors concluded that massage should be considered for the management of cardiovascular surgical postoperative healing and incorporated in post cardiac surgical units (Cutshall, et al, 2010), more research is needed, since it is not currently considered evidence-based therapy. In another study with a very small sample, researchers compared 15 minutes of hand massage to control care (hand holding) followed by 30 minutes of rest for 2-3 sessions in the first 24 hours following cardiac surgery. Patients who received hand massage had lower pain intensity, but vital signs were similar between groups (Boitor, et al, 2015). Although hand massage is a low-cost non- pharmacological intervention that can be safely completed at the bedside (Boitor, et al, 2015), the sample size was too small to provide generalizable evidence. Finally, in a randomized trial, pain and anxiety were assessed after 2 massage therapy or rest (usual care) sessions on day 3 or 4 and day 5 or 6 among 152 cardiac surgery patients (Braun, et al., 2012). The massage group demonstrated a reduction in both pain and anxiety. These studies demonstrate that massage therapy may play a significant role in supporting cardiac patients' wellbeing and healing and that it should be offered along with Reiki therapy to determine if the combination of therapies is more important than 1 complementary therapy alone.

Methodology

Design: Randomized, controlled non-blinded study

Study Groups: Adults who had first-time open heart or robotic-heart surgery involving coronary arteries, cardiac valves or aortic root (+ other procedures).

Inclusion criteria:

- Over 18 years of age

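### A single group size of 20, written in the protocol of an open trial, lets a tally of opened envelopes reveal some group-end allocations: at most about 9%, and about 1% to 2% if assignments become known with a delay

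*Combined protocol and SAP*

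**What the plan says.** Data Collection Procedures sets the sequence. Consent and baseline questionnaires precede allocation: "After preoperative data collection, patients will be randomized to the usual care or intervention group". The method of allocation is then described in these terms: "using envelopes with assignments (136 control subjects 136 experimental subjects); based on groups of 20". No second group size, variation in size or stratification is mentioned. The make-up of a group is not stated. The overall target is equal arms: "The sample size (272 total; 136 per group) was based on a power analysis using the primary outcome" (abstract, Design and Methods).

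The safeguard is in the same section: "Packets will be created by a nurse from the Office of Research and Innovation and envelope assignments will not be shared with any researcher". The section does not say in what order envelopes are used or who opens them.

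The Methodology section gives "Design: Randomized, controlled non-blinded study". Feasibility speaks of one site: "The facility has sufficient trained Reiki certified practitioners to provide these modalities safely and accommodate the sample size". The Intervention section makes the four practitioners members of the research team. Baseline and follow-up questionnaires are handled by staff outside treatment and care ("Research nurses or research coordinators, who are not involved in the intervention or in clinical patient care will administer the questionnaire packets preoperatively"), who return after the last session or usual-care day.

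Separately, the inclusion criteria limit enrolment to four patients a day, two per arm, with surgery on Monday or Tuesday.

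**The concern.** Keeping assignments from researchers protects envelopes that are still closed. It cannot hide opened ones in an open trial where practitioners belong to the research team and questionnaire staff return after treatment. A constant group size turns that history into a forecast: once one arm's places in a group are used up, every remaining place belongs to the other arm.

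The study is offered and consent taken while the next envelope is closed. A recruiter who can infer its content could choose whom to approach or how strongly to encourage them, so that the arms come to differ in patient type. The primary outcomes, depression and anxiety, are self-reported. Adjustment for patient characteristics beyond the baseline score is exploratory only (Data Analysis). Selection of this kind is hard to repair after enrolment.

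**Working it through.** **Yardstick.** The documents give no predictability figure, so the planned effect serves as the scale. From Sample Size: lognormal, CV 1.35, 30% reduction, correlation 0.25.
- Log-scale SD = sqrt(ln(1 + 1.35²)) = 1.019; difference = |ln 0.70| = 0.357; planned effect = 0.357/1.019 = 0.350 SD.
- The two-sample size is 129 (normal approximation) or 130 (exact t). Multiplied by 1 − 0.25² = 0.9375, this gives 121 or 122 per arm, against 123 stated. The inputs are therefore read correctly, and the sample size is not in question.

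**Assumptions for predictability.** Each group of 20 is 10:10. Since 272/20 = 13.6, there are 13 full groups and 12 places left over, taken as 6:6. Envelopes are used in order.

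**Upper bound: every past assignment known at once.**
- In a balanced group of 2m, the expected number of certain allocations is 2m/(m+1). For m = 10 this is 20/11 = 1.82; for m = 6 it is 12/7 = 1.71.
- Trial total: 13 × 20/11 + 12/7 = 25.4 of 272 (9.3%; simulated 95% range 18 to 35).
- The last place is always known; the last two or more in 47% of groups; the last three or more in 21%.
- Expected correct guesses, always naming the arm that is behind, are m + (4^m/C(2m,m) − 1)/2: 12.34 for m = 10 and 7.72 for m = 6. Over the trial this is (13 × 12.34 + 7.72)/272 = 62%, against 50% by chance.

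**Assignments known a day later (four at a time).** Batches of four fit the groups exactly.
- The last batch of a full group is certain if one arm is used up in the first 16: 2·C(16,10)/C(20,10) = 16016/184756 = 0.0867.
- The batch before it is certain if one arm is used up in the first 12: 132/184756 = 0.0007.
- Per full group: 4 × (0.0867 + 0.0007) = 0.350. For the group of 12: 4 × 2·C(8,6)/C(12,6) = 4 × 56/924 = 0.242.
- Total: 13 × 0.350 + 0.242 = 4.8 of 272 (1.8%).

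**Assignments known only for earlier weeks (eight at a time, the Monday and Tuesday maximum).** By simulation, about 2.4 of 272 (0.9%) are certain and 56% of guesses are right.

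**Illustrative imbalance.** Assumption: every recruiter acts on every guess and enrols patients who differ by 0.5 SD according to the predicted arm.

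| Past assignments known | Certain | Imbalance, all guesses |
|---|---|---|
| At once | 9.3% | 0.118 SD |
| A day later | 1.8% | 0.077 SD |
| A week later | 0.9% | 0.060 SD |

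Acting only on certain allocations, the at-once figure is 0.047 SD.

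**How much reaches the outcome.** If selection is on preoperative BSI, an imbalance of 0.118 SD carries 0.25 × 0.118 = 0.03 SD to follow-up (0.03/0.350, about 8% of the planned effect) before adjustment. ANCOVA on that baseline removes it in expectation. Only selection on other traits that affect follow-up mood survives.

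**Effect of varying the size (simulation, past assignments known at once, staff aware of the set of sizes).**

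| Group sizes | Certain | Best guess right |
|---|---|---|
| Fixed 20 | about 9% | 62% |
| Varying 16 to 24 | 0.3% | about 62% |
| Varying 4, 6, 8 | 2.5% | 68% |

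The 0.3% is 0.003 × 272 = 0.8 allocations. Fixing the totals at 136:136 also gives away the end of the last group, about 1.8 more, for a total of 2.6 of 272, still under 1%.

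**The case against.** The strongest reply is that the leak is small and its route uncertain. Most of this stands.

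- **The split is inferred.** Whole groups of 20 do not add up to 272. If 20 is only a packing batch, certainty at the end of each group disappears. The 10:10 reading is natural, but it is an assumption.
- **The visible route is slow.** Questionnaire staff return after three daily sessions or usual-care days that start the day after extubation. By that route, none of a week's assignments is known when that week's other patients are approached. Faster knowledge needs recruiters to see envelopes opened or to hear from practitioners. The documents do not say who opens envelopes, or that those who offer the study are those who return.
- **Twenty is already large.** Small groups would be easier to guess.
- **Varying the size does not cure guessing.** This is correct and limits what the fix can claim.
- **The daily limit may dominate.** If two per arm works as a quota on full days of four, 4/3 of every 4 allocations (33%, about 91 of 272) are certain and guessing is right 71% of the time. Five such days already form a balanced 20, so the group size then adds nothing. This calls for correcting both; the group-size leak remains if the quota is removed.

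A reader might infer that staff will know the last envelope of every group. The documents support only that they could, under the conditions above. Nor do they show that the group size was public during recruitment; it is written in the protocol.

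**Conclusion.** The concern holds in a limited form. One constant group size, stated in the protocol of an open trial at what is in effect one facility, makes some allocations knowable before a patient is approached. The number is at most about 25 of 272 (9%) with immediate and complete knowledge, and about 1% to 2% if knowledge comes a day or a week later. All these figures assume 10:10 groups and envelopes used in order.

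A reader might set the illustrative imbalances of 0.047 to 0.118 SD against the planned 0.350 SD and infer a bias of 13% to 34% of the effect. The documents do not support that as an estimate. It needs immediate knowledge, all recruiters acting alike on a 0.5 SD difference, and selection on a trait that carries fully into follow-up mood and is not captured by baseline BSI. It is a worst case only. The likely bias is modest. The change is worth making because it is nearly free and the damage, if it occurs, cannot be reliably undone.

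**What to change.** In Data Collection Procedures, replace the group-size phrase that ends "using envelopes with assignments (136 control subjects 136 experimental subjects); based on groups of 20" with wording such as: *from a computer-generated 1:1 list in randomly varying, balanced group sizes, with the last group set so that the totals reach 136 and 136; the sizes are held only by the Office of Research and Innovation and are not given in the protocol or to recruiting staff.*

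The instruction to that office, kept in its own file, should require large sizes, for example 16 to 24. Small groups should not be used, because with immediate knowledge they raise best-guess accuracy to about 68%. The amendment should claim only that it removes nearly all certain allocations.

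The cost is one sentence and a different list for the nurse who already makes the packets. The small downside is slightly looser balance at a given moment: the largest possible mid-group difference rises from 10 (group of 20) to 12 (group of 24).

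For full effect, the daily limit in the inclusion criteria must be reconciled with the envelope scheme, by saying whether two per arm is a quota or only a description. It would also help to state that envelopes are used in order and who opens them, since the size of the leak depends on both.

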- Speaks English language and capable of reading and hearing.
- Up to 4 “To Come In” patients enrolled per day (2 standard care and 2 intervention group)
- Arrive for surgery from outpatient (home) environment.
- Scheduled for surgery (arrives in “To Come In” area) on Monday and Tuesday.
- Lives in one of 6 counties of Northeast Ohio, to ensure access post- discharge hospitalization.

Exclusion criteria:

- EPIC history of dementia, cognitive decline, Down's syndrome or other neurologic, psychological or congenital deficiency that impacts ability to make decisions about enrollment. EPIC assessment will occur during the process prior to approaching patients.
- Severe sight and hearing impairment despite assistive devices
- Cardiac surgery on a Wednesday, Thursday or Friday.
- Was not admitted to the hospitals for surgery via To Come In status on the morning of surgery.
- Prolonged intubation (over 48 hours), or reinsertion of an endotracheal tube during or before the intervention is initiated (will result in intervention withdrawal).
- Sedated due to new onset delirium.

Intervention

Reiki is a Japanese energy-based healing technique that has been utilized in the United States since the 1940's. The English translation of Reiki is universal vital energy that flows throughout and encompasses all living forms (Rand, 1991). Reiki is delivered by gentle hand placement either on or slightly above the body by certified Reiki practitioners. In this study, Reiki will be delivered first, for 15 minutes and will involve light placement of hands-on patients' head, chest, shoulders, hands, knees, and feet (~ 3 minutes to each body part).

Manual therapy techniques include light effleurage to head and feet (for 5 minutes; ~ 2.5 minutes to each body part) by the Reiki practitioner who delivered the Reiki therapy. For this research study, manual therapy techniques are defined as light effleurage without pressure.

Reiki and manual therapy will be delivered for 3 consecutive days beginning on the day after endotracheal tube removal. A holistic environment will be provided for healing to both groups.

- Rooms will be quiet, and doors will be closed during the 20 minutes of rest (usual care) or intervention, unless patients are in an ICU setting; in ICU, curtains will be drawn.
- Patients will lie down in bed in supine position or sit in recliner, inhaling through their nose and exhaling through their mouth with their eyes closed.

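### Pain is to be measured at baseline and follow-up, but its planned ANOVA leaves the baseline out: a modest, avoidable loss of precision on a non-primary outcome

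*Combined protocol and SAP*

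**What the plan says.** The summary at the front of the protocol, under Outcome Measures, lists depression and anxiety, then pain, then night-time sleep. It closes the list with the timing "to be measured at baseline and after the last Reiki/manual therapy treatment or 3 days of usual care". The natural reading is that this covers all three, pain included.

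The Data Analysis section then treats them differently. For anxiety, depression and sleep it specifies ANCOVA, "using the follow-up score as the response and patient group and baseline levels of the outcome measure as predictors". For pain it says "Pain, LOS and other continuous factors: will be compared between groups using analysis of variance models". The only other adjustment mentioned is exploratory, for patient characteristics, and baseline pain is not named there.

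Three other places bear on whether a baseline pain score will exist:

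- Outcomes takes pain from routine charting: "Highest (worst) and lowest (least) pain in the past 24 hours will be assessed via pain scores recorded in EPIC".
- Data Collection Procedures describes the packet given before surgery and after the intervention as being "for the following data: anxiety and depression and sleep". Pain is not in it. The same section says "After preoperative data collection, patients will be randomized to the usual care or intervention group".
- The inclusion criteria require that patients "Arrive for surgery from outpatient (home) environment".

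**The concern.** Length of stay and narcotic dose have no planned baseline, so ANOVA suits them. By the summary, pain does have one, yet it is grouped with those outcomes. The plan already accepts the case for adjustment, because its sample size takes credit for the ANCOVA variance reduction on the primary outcomes.

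Without the baseline term, the interval for research question 3 may be wider than the planned data allow, and any chance imbalance in baseline pain stays in the estimate. Neither makes the test biased or invalid, and the primary conclusion on depression and anxiety is untouched. If adjustment were added only after the data had been seen, the choice could look data-driven, so it is better settled beforehand.

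**Working it through.** **Inputs.** From Sample Size: 123 evaluable per group, 136 recruited, correlation ρ = 0.25 (for the Brief Symptom Inventory), coefficient of variation 1.35, 30% reduction in mean, two-sided 0.05, 80% power. No correlation is given for pain, so ρ = 0.10 and 0.50 are assumptions that bracket 0.25. I also assume 123 per group are evaluable for pain.

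**Reproducing the plan's figure.**

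- Log-scale SD = √ln(1 + 1.35²) = 1.0186.
- Log-scale difference = |ln 0.70| = 0.3567.
- A two-sample comparison needs 129 per group (normal approximation) or 130 (t-test).
- Multiplying by 1 − 0.25² = 0.9375 gives 120.9 or 121.9, so 121 or 122 against the stated 123. Power at 123 is 80.6%.
- 123 × 1.10 = 135.3, rounded up to 136.

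The plan's figure is therefore confirmed, and so is its use of the factor 1 − ρ².

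**The same factor applied to pain, complete baselines.** ANCOVA variance = (1 − ρ²) × ANOVA variance. Interval width scales by √(1 − ρ²), and the ANOVA sample size giving equal precision is 123/(1 − ρ²).

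| ρ | 1 − ρ² | Interval width factor | Equivalent n per group | ANOVA power where ANCOVA has 80% |
|---|---|---|---|---|
| 0.10 | 0.99 | 0.995 | 124 | 79.6% |
| 0.25 | 0.9375 | 0.968 | 131 | 77.4% |
| 0.50 | 0.75 | 0.866 | 164 | 67.9% |

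**Missing baselines.** Let m be the share missing, at random.

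- If patients without a baseline are dropped, the variance relative to ANOVA is (1 − ρ²)/(1 − m). This reaches 1 when m = ρ², so the gain is gone once 123 × ρ² = 1.2, 7.7 or 30.8 baselines per group are missing (ρ = 0.10, 0.25, 0.50).
- If missing baselines are set to the pooled mean and flagged by an indicator, everyone is kept and the gain is about (1 − m)ρ². At m = 0.30 that is 0.7 × 0.0625 = 4.4% for ρ = 0.25, 0.7 × 0.25 = 17.5% for ρ = 0.50, and 0.7 × 0.01 = 0.7% (in effect nil) for ρ = 0.10.

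A simulation (123 per group, 8,000 runs) gave these variances relative to ANOVA, in line with the formulas:

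| Missing | Method | ρ = 0.10 | ρ = 0.25 | ρ = 0.50 |
|---|---|---|---|---|
| 10% | Drop patients | 1.11 | 1.06 | 0.83 |
| 10% | Mean plus indicator | 1.00 | 0.95 | 0.76 |
| 30% | Drop patients | 1.43 | 1.33 | 1.09 |
| 30% | Mean plus indicator | 1.01 | 0.97 | 0.84 |

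Bias was below 0.003 SD for every method. A further simulation (6,000 runs) took mean plus indicator to heavier missingness. At 70% missing, the variance falls by about 1% at ρ = 0.25 and not at all at ρ = 0.10. At 90% missing, there is no gain at ρ = 0.10 or 0.25 and about 2% at ρ = 0.50. The most the method costs at 70 to 90% missing is about 1% of variance.

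**The case against.** The strongest reply is that the pain baseline may not really exist. It rests on one timing clause in the summary, placed after the sleep item. The operative sections schedule no preoperative pain score, and patients who come from home on the morning of surgery may have none in EPIC, still less a 24-hour highest and lowest. On that view ANOVA fits the data that will be collected, and the larger gains need both a high correlation and nearly complete baselines.

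Much of this stands as a limit on the size of the gain, which may be nil. It does not remove the inconsistency: the summary promises a baseline that no later section defines or uses. It is also the reason a bare switch to ANCOVA would be poor advice, since dropping patients without a baseline can do worse than ANOVA.

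Two further points are fair. First, the plan does not say whether the ANOVA response is the follow-up value or the change. If it is change, and the two variances are equal, its variance is 2(1 − ρ) times that of the follow-up value: 1.8, 1.5 and 1.0 at ρ = 0.10, 0.25 and 0.50. The loss against ANCOVA would then be larger than shown above. Second, the documents do not say whether baseline pain means before surgery or before the first session. A pre-randomisation score matches how the other scales are handled in Data Collection Procedures. If only one score exists, it is both the highest and the lowest recorded, though it may predict postoperative pain less well than a like-for-like measure.

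**Conclusion.** The concern holds as an optional improvement. Pain is planned with a baseline, and its analysis leaves that baseline out. The cost is precision, not validity. With complete baselines the interval could be 3.2% narrower at ρ = 0.25, within a range of 0.5% to 13% for ρ from 0.10 to 0.50. Missing baselines shrink this, possibly to nothing. The figures assume 123 evaluable patients per group, baselines missing at random, and correlations for pain that the documents do not supply. That pain is secondary is inferred from depression and anxiety being the only outcomes called primary.

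**What to change.** In Data Analysis, replace the pain part of the ANOVA sentence with:

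> Pain (0–10 intensity, highest in 24 hours and lowest in 24 hours, each analysed separately): ANCOVA with the follow-up value as response, and group and the baseline value of the same measure as predictors. Baseline is taken from EPIC pain scores recorded before randomisation; if only one score exists, it is the covariate in all three models. A missing baseline is set to the mean of the observed baselines pooled over both groups, with a missing indicator in the model, so that no patient is dropped. The number of missing baselines is reported by group.

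Keep ANOVA for length of stay and narcotic dose. If the investigators find that no usable preoperative pain score is recorded, they should say so and remove pain from the baseline timing in the summary; ANOVA of the follow-up value is then appropriate.

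The cost is a few sentences, the pre-randomisation pain score added to the EPIC request, one or two degrees of freedom and a little extra analysis. No extra patients or patient contact are needed. The change should be made before outcome data are seen.
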